12.3 Data Analyses Plans

For this single group trial, summary frequencies and statistics will be provided for all relevant patient characteristics and clinical measures, including demographics (e.g., age, cancer stage, educational attainment, etc) as well as clinical outcomes (e.g., laboratory monitoring, adverse event monitoring, etc.). These include valid counts with percentages for categorical and ordinal variables as well as median with interquartile range or mean with standard deviation or standard error for continuous variables.

For the primary aim, a one-tailed one-sample test for proportions will be used to test whether the observed toxicity rate is lower than the hypothesized toxicity rate. For relapse-free survival, death will *not* be considered a competing event.

Instead, a two-sided one-sample log-rank test will be used to estimate the probability of being relapse free 24 months following treatment.

The instantaneous risk of relapse or death may be estimated as a function of age, cancer stage, and other covariates using semi-nonparametric Cox proportional hazards models. For these models, the number of covariates used for the adjustment will be determined by the number of events. Approximately one predictor for every 10 relapse or mortality events may be used to determine adjusted survival probabilities as described by Peduzzi et al.²⁴ For all Cox proportional hazards models, the proportional hazards assumption will be evaluated using Martingale residuals as described by Lin, Wei, and Ying.²⁵ If the proportional hazards assumption is violated, parametric accelerated failure time models may be used assuming the true underlying hazard distribution is identified.

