Biostatistician
Division of Biostatistics
Clinical Research Office, Loyola University Chicago
[name]
[name]
Email: [contact]

Research Office: Clinical Research Office (CRO)
Stritch School of Medicine, Loyola University Chicago
[name]
[name]
[name]
[contact]
[contact]

LU 210546

Version 10/23/17

Signature Page

The signature below constitutes the approval of this protocol and the attachments, and provides the necessary assurances that this trial will be conducted according to all stipulations of the protocol, including all statements regarding confidentiality, and according to local legal and regulatory requirements and applicable U.S. federal regulations and ICH guidelines.

Principal Investigator (PI) Name: _____

PI Signature: _____

Date: _____

[figure not shown]
STUDY SUMMARY	
Title	BEACON - A phase I/II study of high-dose-rate Brachytherapy and External beam and short-term Androgen deprivation CO mbined for the treatment of Men with Fluciclovine PET Pelvic Nodal Uptake in locally recurrent prostate cancer after prior definitive radiotherapy
Short Title	Combined salvage high dose rate brachytherapy, external beam and short-term hormonal therapy for local recurrent prostate cancer with fluciclovine PET uptake in pelvic nodes after radiotherapy
Protocol Number	***
Methodology	Phase I/II Non-randomized trial
Study Duration	5 years
Study Center(s)	Loyola University medical Center, Stritch School of Medicine, Loyola University Chicago
Objectives	
 1. To determine the 3 month grade ≥ 3 radiation-related genitourinary and gastrointestinal toxicity of this treatment approach (primary endpoint) 2. To describe the acute and late toxicity profile with this approach 3. To evaluate disease control efficacy outcomes (biochemical progression-free survival, local control, regional recurrence, cause-specific survival, overall survival, etc.) 4. To evaluate patient reported health related quality of life following this treatment approach 5. To describe the dosimetry in patients undergoing this approach
Number of Subjects	24

LU 210546

Version 10/23/17

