2.0 STUDY OBJECTIVES

2.1 *Primary Objective*

2.1.1 To determine the incidence of acute grade ≥ 3 radiation-related genitourinary (GU) and gastrointestinal (GI) toxicity of this treatment approach

2.2 *Secondary Objectives*

- 2.2.1 To describe the acute and late toxicity profile with this approach
- 2.2.2 To evaluate disease control efficacy outcomes (biochemical progression-free survival, local control, regional recurrence, cause-specific survival, overall survival, *etc.*)
- 2.2.3 To evaluate patient reported health related quality of life following this treatment approach
- 2.2.4 To describe the dosimetry in patients undergoing this approach

2.3 *Endpoints*

2.3.1 Primary Endpoint:

2.3.1.1 3-month radiation-related grade ≥ 3 GU and GI toxicity as defined by Common Terminology Criteria for Adverse Events (CTCAE) v4.03 (Link available in Appendix A).

2.3.2 Secondary Endpoints:

2.3.2.1 All-grade acute and late toxicity as defined by CTCAE v4.03 criteria (see Appendix A)

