8.1.11 Labs

AST, ALT, Alkaline Phosphatase, and any labs required for the brachytherapy procedure as part of usual care.

8.2 *Follow-up Procedures*

Patients will be followed as described in Section 8.3.

8.3 *Study Parameters*

	Pre-study	Start of EBRT	Week 4 post-treatment	Month 3 & 6	Month 12	Follow-up Q 6 months*	Time of Biochemical Recurrence
Informed Consent	X						
History and PE, including DRE	X		X	X	X	X	
Medication Assessment	X		X	X	X	X	
Performance Status	X		X	X	X	X	
Toxicity Assessment			X	X	X	X	
PSA	X			X	X	X	
Bone scan	X						X
MP-MRI	X						X¥
PET/CT	X						
IPSS score	X		X	X	X	X	
EPIC-26	X		X	X	X	X	
AST/ALT/ALK PHOS	X	X					

* Until disease progression, death, or follow up period is complete

¥If MP-MRI reveals any suspicious lesions, then biopsy is encouraged.

DRE – Digital Rectal Exam

PE – Physical Exam

MP – Multi-parametric

EBRT – External Beam Radiotherapy

8.4 *Removal of Subjects from Study*

Patients can be taken off the study treatment and/or study at any time at their own request, or they may be withdrawn at the discretion of the investigator for safety, behavioral, or administrative reasons. The reason(s) for discontinuation will be documented and may include:

- 8.4.1 Patient voluntarily withdraws prior to treatment;
- 8.4.2 Patient withdraws consent (termination of treatment and follow-up);
- 8.4.3 Patient is unable to comply with protocol requirements;
- 8.4.4 Patient develops interval co-morbidity that makes continuation in the protocol unsafe;
- 8.4.5 Treating physician(s) judge(s) the study would not be in the patient's best interest;
- 8.4.6 Development of second malignancy (except for basal cell carcinoma or squamous cell carcinoma of the skin) that requires treatment, which would interfere with this study;
- 8.4.7 If a research subject cannot be located to document survival after a period of 2 years; the subject may be considered "lost to follow-up". All attempts to contact the subject during the two years must be documented and approved by the Data Monitoring Committee.

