9.0 MEASUREMENT OF EFFECT

9.1 *Antitumor Effect- Solid Tumors*

9.1.1 Definitions:

Evaluable for toxicity: All patients will be evaluable for toxicity immediately following brachytherapy.

Evaluable for disease control assessment: All patients with at least 2 follow-up PSAs will be evaluable for disease control. After brachytherapy, these patients will have their disease status classified according to the definitions stated below.

Biochemical (PSA) recurrence (BR): Based on RTOG Phoenix definition: an increase of the PSA level at least 2 ng/ml greater than the minimum level after therapy (REF: phoenix paper)

All patients with BR should undergo at least MP-MRI of the prostate and bone scan. Biopsy of any suspicious lesions within the prostate gland on MP-MRI is encouraged.

Freedom from Biochemical (PSA) Recurrence (FFBR):

The time to PSA failure will be measured from the date of treatment to the date of a rise by 2 ng/mL or more above the nadir PSA. The time of failure will be the date of the first PSA that is 2 ng/mL or more above the lowest prior post-treatment PSA value. If the rise in PSA to $>$ nadir + 2 occurs during the first 36 months followed by a subsequent non-hormonal induced PSA decrease, patients will **not** be considered PSA failures.

As a benign “spike” or “bounce” in the PSA value has been described in as many as 35% of patients 12-36 months following brachytherapy, intervention for a PSA failure should be based on a positive prostate biopsy at least 24 months post-treatment and/or clinical evidence of distant relapse (i.e., bone scan, CT scan, etc).

Local Failure (LF): This rating will be assigned when there is biopsy-proven disease progression or recurrence at the lesion within the prostate treated with protocol therapy. Histologic criterion for local failure is the presence of prostatic carcinoma upon biopsy more than 2 years after the start of treatment. Residual carcinoma on biopsy should show minimal radiation effect and should be in clinical scenario of increasing PSA.

Local Control (LC): Absence of local failure. This will be assumed in patients with a controlled PSA and for those with PSA failure but no radiographic, clinical, or biopsy-proven disease at the lesion treated with protocol therapy.

Freedom from Local Failure (FFLF): The time to local progression will be measured from the date of treatment to the date of local failure.

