12.0 STATISTICAL CONSIDERATIONS

12.1 *Study Design/Study Endpoints*

The primary outcome will be any radiotherapy-related acute or chronic grade 3-5 toxicity as defined previously in the document. The study is designed as a two stage Phase II study as described below.

12.2 *Sample Size and Accrual*

Primary Aim

In this single-arm oncology trial evaluating the safety and efficacy of HDR brachytherapy for recurrent prostate cancer, one goal is to determine the toxicity

of single fraction focal treatment. Simon's two-stage²³ design is used to power this aim. The primary hypothesis is that the acceptable toxic response rate is less than or equal to 10.0% (p_1). The unacceptable toxic rate is set at 33% (p_0).

More concisely:

$$H_0: p_0 \geq .33$$

$$H_A: p_1 \leq .10$$

The null hypothesis is that the unacceptable toxic response rate is at least 33%. This will be tested against a one-sided alternative that the toxicity rate is 10% or less.

In the first stage, 7 patients will be accrued. If there are 2 or more toxic responses (radiation-related acute grade ≥ 3 GU or GI toxicity) in these 7 patients, the study will be stopped for safety reasons. Otherwise, 17 additional patients will be accrued for a total of 24 patients. Note that, under these conditions, the probability of stopping early is 73% if the toxic response rate is truly higher than 10.0%.

At the end of the second stage, the null hypothesis that the toxicity rate is 33% or higher will be rejected if more than 19 (non-toxic) responses are observed in 24 patients. When the true toxicity rate is 10.0%, this design yields a type I error rate of .046 and power of 81%.

Secondary Aim

We also will describe the freedom from biochemical recurrence, relapse-free survival, local control, elsewhere-prostate control, freedom-from local failure, freedom from distant metastasis, freedom from hormonal therapy, disease-free survival, cause-specific survival, and overall survival.

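### Late toxicity is a secondary endpoint but is planned only as crude percentages, which have no time horizon when follow-up differs between men

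*Combined protocol and SAP*

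**What the plan says.** Section 2.3.2.1 lists as a secondary endpoint "All-grade acute and late toxicity as defined by CTCAE v4.03 criteria". It gives no date at which late begins and no time at which a late rate is to be reported. The primary endpoint in 2.3.1.1, by contrast, has a window: "3-month radiation-related grade ≥ 3 GU and GI toxicity as defined by Common Terminology Criteria for Adverse Events".

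The table in 8.3 schedules toxicity assessment at week 4, at months 3, 6 and 12, and then every 6 months. A footnote to the 6-monthly column ends those visits as follows: "Until disease progression, death, or follow up period is complete". The length of the follow-up period is not stated. The study summary gives a 5-year duration and does not divide it between accrual and follow-up.

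Section 9.1.1 sets no minimum follow-up for toxicity: "All patients will be evaluable for toxicity immediately following brachytherapy".

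Section 12.3 includes among the items to be summarised "clinical outcomes (e.g., laboratory monitoring, adverse event monitoring, etc", and the summary for categorical and ordinal variables is "These include valid counts with percentages for categorical and ordinal variables as well as median with interquartile range". Its other analysis of toxicity is the one-sample test for the primary aim. The log-rank, Cox and accelerated failure time methods are tied to relapse or death.

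**The concern.** Counts and percentages suit the 3-month endpoint, because each man has the same window. Late toxicity accumulates for as long as a man is observed. If a man followed for under a year and a man followed for several years enter the denominator alike, the percentage mixes risks over different lengths of time. It answers no question of the form *what is the risk by month t*, and the same treatment would give a different figure under another accrual rate or data cut.

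This matters because late effects are a central risk of re-irradiation. In the phase II HDR series cited in the background, the grade 3 urinary events described are late ones (incontinence in 1 of 42, strictures in 3). Section 1.5 says these data should support a phase III trial, whose planning needs a rate at a named time. Section 12.3 already names a 24-month time for relapse-free survival, so it takes account of time for efficacy but not for late harm.

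**Working it through.** **The plan's own figures.** The documents give none for late toxicity. The two-stage figures reproduce: continuing with at most 1 toxicity in 7 and rejecting the null with at most 4 in 24 gives an exact type I error of 0.0462 at a 33% rate (stated .046) and power of 80.9% at 10% (stated 81%). These concern acute toxicity and do not bear on this point.

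**Inputs for an illustration.** From the documents: the 60-month study, and 51% biochemical control at 5 years in the cited retrospective HDR series. Assumed, because the documents are silent: 15% true late toxicity at 24 months with a constant hazard, uniform accrual over A = 24, 36 or 48 months, and 4 months from registration to the end of radiotherapy. For simplicity the hazard runs from the end of radiotherapy, and deaths are ignored.

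**Formulas.**
- Hazard: h = −ln(0.85)/24 = 0.00677 per month.
- True incidence by month t: F(t) = 1 − exp(−ht). F(12) = 7.8%, F(24) = 15.0%, F(48) = 27.8%.
- Potential follow-up f is uniform from 56 − A to 56 months (8 to 56 months for A = 48).
- Crude percentage with an event by t: the mean of F(min(f, t)). It is below F(t) whenever some men have f < t.
- Crude percentage over all follow-up: the mean of F(f). It lies between F at the shortest and F at the longest follow-up, so it can exceed F(12) or F(24).

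**Numbers for A = 48.**
- By 24 months: two thirds of men (32/48) have at least 24 months and contribute 0.667 × 0.15 = 0.100. The rest contribute [16 − (e^(−8h) − e^(−24h))/h]/48 = 0.034. The sum is 13.4%.
- By 12 months: 44/48 × 0.0780 + 0.0055 = 7.7%, against 7.8%.
- All follow-up: 1 − (e^(−8h) − e^(−56h))/(48h) = 1 − (0.9473 − 0.6844)/0.3250 = 19.1%.

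**If visits also stop at progression.** The progression hazard is −ln(0.51)/60 = 0.0112 per month, taken as independent of toxicity. Assessment ends at the later of progression and month 12, because the footnote applies only to the 6-monthly visits. These figures were simulated.

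| Accrual | By 12 mo | By 24 mo | All follow-up | By 24 mo, stop at progression | All follow-up, stop at progression |
|---|---|---|---|---|---|
| 24 mo | 7.8% | 15.0% | 25.7% | 13.7% | 21.0% |
| 36 mo | 7.8% | 14.9% | 22.5% | 13.6% | 18.8% |
| 48 mo | 7.7% | 13.4% | 19.1% | 12.4% | 16.3% |
| True | 7.8% | 15.0% | no fixed time | 15.0% | no fixed time |

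The same true hazard thus gives an all-follow-up percentage anywhere from 16.3% to 25.7%, depending only on accrual and on when visits stop.

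**The case against.** A reader might infer that the plan understates late toxicity outright. The documents do not support that. At matched times the shortfall is small: 13.4% or 12.4% against 15% is 0.4 or 0.6 of a man in 24 (24 × 0.016; 24 × 0.026), while the standard error of a 15% proportion is √(0.15 × 0.85/24) = 7.3 points. The all-follow-up figures all lie above the assumed 24-month rate. Setting 16% to 19% against a 48-month incidence of 27.8% makes the gap look large, but no passage names 48 months, and with 48-month accrual only 1 man in 6 (8/48) would be followed that long. Reporting when the last man reaches month 3 would lower the 24-month figure to 9.5% (24-month accrual) or 11.3% (36-month accrual), but nothing in the plan says late toxicity will be reported then.

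A reader might also infer that crude figures could not be compared with other series. The background cites late events from the phase II HDR series as simple counts, alongside a stated median follow-up. Crude counts with follow-up given would match that.

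Two further points are fair. Section 12.3 never names late toxicity, and *valid* may mean non-missing denominators, so percentages at each visit would fit its wording. The objective in 2.2.1 is only descriptive, with no test attached.

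What remains is this. Percentages per visit give prevalence among men still assessed, not the risk of ever having had the event. Under either reading, no method for late toxicity takes account of how long a man was observed, and the plan commits to no horizon and no statement of follow-up.

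**Conclusion.** The point holds in a limited form. The planned summary does not fix a time for the late toxicity rate, and a crude percentage would depend on accrual and the data cut. That follows from 2.3.2.1, 8.3 and 12.3 whatever the true rate. The downward bias applies in expectation to a percentage counted up to a time that some men have not reached. Under the assumptions above it ranges from nothing to 2.6 points at 24 months (12.4% to 15% against 15%) and is at most 0.1 point at 12 months. All of this rests on an assumed rate, accrual pattern and lag, and on progression being independent of toxicity; the trial's own figure cannot be computed from the documents.

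The primary test is unaffected if 2.3.1.1 governs. Section 12.1, however, describes the primary outcome as "any radiotherapy-related acute or chronic grade 3-5 toxicity as defined previously in the document". If that governed, the missing horizon would reach the primary test as well. The documents contradict each other here and do not show which is meant.

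**What to change.** In 12.3, keep counts with percentages for acute (3-month) toxicity. For late toxicity:

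- Define late as an event after the 3-month acute window, with time counted from the end of radiotherapy.
- Estimate the cumulative incidence of the first late grade ≥2 and of the first late grade ≥3 GU and GI event, with death as a competing event and censoring at the last toxicity assessment.
- Report at 12 and 24 months with 95% confidence intervals and numbers at risk, and give the median follow-up.
- State that ending scheduled assessment at progression may be informative censoring, which this estimator does not remove.

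Reconcile 12.1 with 2.3.1.1 on whether chronic toxicity belongs to the primary outcome.

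The cost is a paragraph of plan text and a few lines of code on assessments already scheduled in 8.3; no visit or treatment changes. With 24 men the intervals will be wide, and the late figure may be slightly less favourable than a crude percentage.

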Diagnosis and Main Inclusion Criteria	
 • Biopsy-proven local recurrence of prostate adenocarcinoma (biopsy within 182 days) • Pathologic Fluciclovine uptake in pelvic lymph nodes without distant metastases • Current AUA International Prostate Symptom Score (IPSS) score <20 • Initial disease stage cT1-3a NX or N0 • Treated with prior definitive radiation therapy using any radiotherapeutic modality (prior whole pelvis RT ineligible)
Duration of Administration	2 brachytherapy implants, ~5-8 weeks of daily radiation, 6 months hormonal therapy
Statistical Methodology	
This study is designed as a two stage Phase I/II, non-randomized study. In the first stage, 7 patients will be accrued. If there are 2 or more toxic responses in these 7 patients, the study will be stopped for safety reasons. Otherwise, 17 additional patients will be accrued for a total of 24 patients.
 
Assuming that the true toxicity rate in the population is 10% or less, the study is powered to reject the null hypothesis that the toxicity rate is 33% or higher. A toxicity event is defined as an acute grade ≥ 3 radiation-related toxicity as assessed by the Common Toxicity Criteria for Adverse Events version 4.
 
Standard non-parametric or parametric methods will be used to describe these patients' demographic and clinical information as well as their dosimetric information. The primary aim of the study is to estimate the toxicity rate of HDR brachytherapy among patients with recurrent prostate cancer. A one-tailed test for a difference in proportions will be used to determine whether the observed toxicity rate is lower than the hypothesized toxicity rate. The null hypothesis that the toxicity rate is 33% or higher will be rejected if more than 19 (non-toxic) responses are observed in 24 patients. When the true toxicity rate is 10.0%, this design yields a type I error rate of .046 and power of 81%.
 
We also will describe the freedom from biochemical recurrence, relapse-free survival, local control, elsewhere-prostate control, freedom-from local failure, freedom from distant metastasis, freedom from hormonal therapy, disease-free survival, cause-specific survival, and overall survival.

Study Schema

LU 210546

Version 10/23/17

Table of Contents

Title page.....	i
Signature page.....	iv
Study Summary.....	v-vi
Study Schema	vii
List of Abbreviations	x
1.0 Background and Rationale	1
1.1 Disease Background and Lessons from Other Malignancies	1

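### Section 12.3 names a one-sample proportion test for the primary aim without tying it to the two-stage boundary in 12.2; at exactly 4/24 toxicities some forms of that test give p above .05 where the boundary rejects

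*Combined protocol and SAP*

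**What the plan says.** Section 12.2 sets a Simon two-stage design. On the null rate: "The unacceptable toxic rate is set at 33"%. On the alternative: "The primary hypothesis is that the acceptable toxic response rate is less than or equal to 10.0"%. Seven patients enter first. With 2 or more toxicities "in these 7 patients, the study will be stopped for safety reasons"; otherwise 17 more enter, for a total of 24. At the end, the null hypothesis "will be rejected if more than 19 (non-toxic) responses are observed in 24 patients", which means at most 4 toxicities. Section 12.2 adds that, at a true 10% rate, "this design yields a type I error rate of .046 and power of 81"%.

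Section 12.3 covers the primary aim in one sentence: "a one-tailed one-sample test for proportions will be used to test whether the observed toxicity rate is lower than the hypothesized toxicity rate". It mentions no stages, boundary, exact or approximate form, or significance level.

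The Study Summary (Statistical Methodology) has both elements in adjacent sentences. First: "A one-tailed test for a difference in proportions will be used to determine whether the observed toxicity rate is lower" than the hypothesized one. Then: "The null hypothesis that the toxicity rate is 33% or higher will be rejected if more than 19 (non-toxic) responses" are seen in 24 patients. It does not say that the second sentence is how the first is carried out.

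**The concern.** An analyst working from 12.3 would run a standard one-sample test on the final count out of 24. Its reference distribution includes sequences with 2 or more toxicities among the first 7, and the stage 1 stop rules those out. The p-value can then differ from the one implied by the design. At the edge of the rejection region it can fall on the other side of .05.

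Two things would be at stake. The report could reject the null by the 12.2 rule and print a primary p-value that says the opposite. And because the form of the test is open, it could be chosen after the count is known, at the one result where the choice matters.

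**Working it through.** **Inputs.** From 12.2: p0 = 0.33, p1 = 0.10, n1 = 7, continue with 0 or 1 toxicities, n2 = 17, reject with at most 4 of 24. Assumptions: the hypothesized rate in 12.3 is 33%, and the level for its test is one-sided .05, since 12.3 gives none.

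**Step 1: reproduce the plan's figures.** The probability of rejecting at true rate p is

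P(reject) = Σ over i = 0, 1 of P(Bin(7, p) = i) × P(Bin(17, p) ≤ 4 − i).

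- p = 0.33: 0.0606 × 0.2913 + 0.2090 × 0.1366 = 0.0177 + 0.0285 = 0.0462. The plan states .046.
- p = 0.10: 0.4783 × 0.9779 + 0.3720 × 0.9174 = 0.4677 + 0.3413 = 0.8090. The plan states 81%.

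The stated operating characteristics therefore belong to the two-stage rule, and they are right.

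**Step 2: p-values at and around the boundary.** For x toxicities in 24 and p0 = 0.33:

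- Two-stage p: the sum in step 1 with 4 replaced by x.
- Exact: P(Bin(24, 0.33) ≤ x).
- Mid-p: the exact p minus half of P(Bin(24, 0.33) = x).
- Score z: (x/24 − 0.33) / √(0.33 × 0.67/24), with denominator 0.0960.
- Continuity-corrected z: the score z with 1/48 added to x/24.
- Wald z: the score z with x/24 in place of 0.33 in the standard error.

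At x = 4, for example, the score z is (0.1667 − 0.33)/0.0960 = −1.70 and the corrected z is (0.1875 − 0.33)/0.0960 = −1.48.

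| One-sided p | 3/24 | 4/24 | 5/24 |
|---|---|---|---|
| 12.2 rule | reject | reject | do not reject |
| Two-stage | 0.0181 | 0.0462 | 0.0905 |
| Exact binomial | 0.0215 | **0.0634** | 0.1459 |
| Continuity-corrected z | 0.0275 | **0.0688** | 0.1467 |
| Score z | 0.0163 | 0.0444 | 0.1025 |
| Mid-p | 0.0134 | 0.0425 | 0.1047 |
| Wald z | 0.0012 | 0.0159 | 0.0711 |

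Only the two bold entries disagree with the rule. Both also exceed the design's own .046. With p0 = 1/3 they are 0.0594 and 0.0648, so the conclusion is the same.

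**Step 3: source of the gap.** Exact minus two-stage p at 4/24 is 0.0634 − 0.0462 = 0.0172. This equals P(at least 2 of the first 7 and at most 4 of 24) at 33%, which is the set of paths that the stop removes.

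**Step 4: how often 4/24 arises.** P(continue and exactly 4 of 24) is 0.0868 at a 10% rate, 0.1401 at 15% and 0.0281 at 33%.

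**Step 5: if the exact or corrected p-value at .05 overrode the boundary.** Rejection would need at most 3 of 24 within the same two-stage scheme.

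| True rate | Reject at ≤ 4 | Reject at ≤ 3 |
|---|---|---|
| 10% (power) | 80.9% | 72.2% |
| 15% (power) | 58.8% | 44.8% |
| 33% (type I error) | .046 | .018 |

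**The case against.** The protocol holds only one rejection criterion, the 12.2 boundary, and the Study Summary repeats it. A sentence in 12.3 with no threshold does not displace it. In the Summary the test sentence stands directly before the boundary and its error rates, so the boundary can be read as the way the test is carried out. The term fixed-sample is an interpretation of 12.3, not its wording. The conflict also needs an exact or corrected form and a .05 level, and three of the five usual forms agree with the rule. Finally, no passage promises a p-value.

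Most of this stands, and it limits the point. A reader might infer that 12.3 replaces the 12.2 rule, so that the trial really has 72.2% power. The documents do not support that, because nothing lets a p-value override the boundary. Nor is there a case for inflated type I error from the exact or corrected forms, which err on the conservative side.

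The objection does not remove the gap itself. Section 12.3 is the analysis section, and it omits both the boundary and the stages. The Summary places test and boundary together without equating them. Even if the boundary plainly decides, a test run as 12.3 describes can still yield a p-value that contradicts it.

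**Conclusion.** The point holds as a gap between 12.2 and 12.3 and should be corrected. The design is sound and its figures reproduce. The analysis section names a test that, on its plain reading, ignores the stage 1 stop, and it leaves the form and level open.

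The effect is confined to 4/24. There the available one-sided p-values run from 0.016 to 0.069, against a two-stage value of 0.046. The likely harm is a conservative primary p-value printed beside a correct rejection. The fall in power in step 5 is conditional on an override that the protocol does not state.

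This rests on reading 12.3 as a fixed-sample test, on a null rate of 33%, and on an assumed one-sided level of .05.

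**What to change.** In 12.3 and in the Study Summary, replace the test sentence with wording such as: *The primary hypothesis is decided by the two-stage boundary in 12.2. Any p-value reported after stage two is computed from the two-stage sampling distribution, as the probability at a 33% rate of at most 1 toxicity in the first 7 and at most the observed total in 24.*

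At 4/24 this gives 0.046, which agrees with the decision and equals the stated type I error. The change should be made before the primary data are analysed.

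The cost is one sentence in two places and a few lines of code. Patients, data collection, stopping rule and sample size stay as they are.
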